7.7 LOST TO FOLLOW-UP

A subject will be considered lost to follow-up if he/she does not appear for the scheduled study visit for 2 consecutive visits, and study personnel are unable to contact the subject.

Some actively enrolled subjects will not return for follow-up exams on time. Study personnel must make a reasonable effort to contact the subject and document the following contact attempts before declaring a subject to be lost to follow-up: the subject has been contacted according to the site's policies, but no fewer than two documented phone contacts (at least one of these attempted phone contacts conducted by the Investigator) and one written attempt without response. The written attempt can either be a certified letter or an email with read confirmation dependent on accepted ways of communication within the study regions. Copies of all attempts to reach the subjects by mail or email and/or the attempts to contact the subject via other means should be documented, and that documentation should be kept with the subject’s source documents.

CONFIDENTIAL AND PROPRIETARY

This document contains information that is confidential and proprietary to Smith & Nephew PLC and Smith & Nephew, Inc. and is intended for use only by Smith & Nephew and its manufacturer. It shall not be reproduced or copied in whole or in part, nor shall the contents be disclosed by any means without prior written permission from Smith & Nephew, nor shall anyone make any use of it that is contrary to the expressed or implied wishes of Smith & Nephew.

Clinical Protocol	Study Number: OR3O.2019.10 (China)
Prospective, Multi-center, Randomized, Controlled Study to Evaluate the Safety and Efficacy of the OR3O™ Dual Mobility System versus conventional single bearing design Total Hip System in Primary Total Hip Arthroplasty (THA) Procedures	Version: 1.0, 18Aug2020
	Page: 34 of 90

7.8 WITHDRAWAL

7.8.1 Withdrawal from Treatment

Subjects may be withdrawn from having the study device implanted at a date close to surgery or during surgery for the following reasons:

- At the discretion of the Investigator due to:
 - A change in treatment being clinically warranted.
 - An adverse event.
 - Any other significant reason identified by the Investigator.

Subjects who provide informed consent but do not receive the study device for any reason will be considered a Screen Failure. Screen Failures will not count into the total number of enrolled subjects.

If at any point during the study, the study device needs to be revised for any reason the following will apply: Intraoperative data from the revision surgery will be collected including implant information used for revision THA. Subjects will terminate the study following revision surgery. Subjects shall be followed by the Investigator according to sites' standard of care in order to monitor the subject's health status and the outcome of the revision. Data collected following the revision surgery will be reported as follow-up data to the adverse event. Data will not be included as study data but presented separately as safety data. Data collected upon the point of revision will be included as study data.

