7.8.2 Withdrawal from Study

The Investigator may withdraw subjects from the study, including but not limited to the following reasons:

- Subject noncompliance (e.g., did not follow instructions for regular follow up);
- Subject lost to follow-up;
- The Investigator or the Sponsor stops the study for any reason and decides to withdraw subject(s) from the study;
- Concurrent illness;

CONFIDENTIAL AND PROPRIETARY

This document contains information that is confidential and proprietary to Smith & Nephew PLC and Smith & Nephew, Inc. and is intended for use only by Smith & Nephew and its manufacturer. It shall not be reproduced or copied in whole or in part, nor shall the contents be disclosed by any means without prior written permission from Smith & Nephew, nor shall anyone make any use of it that is contrary to the expressed or implied wishes of Smith & Nephew.

Clinical Protocol	Study Number: OR3O.2019.10 (China)
Prospective, Multi-center, Randomized, Controlled Study to Evaluate the Safety and Efficacy of the OR3O™ Dual Mobility System versus conventional single bearing design Total Hip System in Primary Total Hip Arthroplasty (THA) Procedures	Version: 1.0, 18Aug2020
	Page: 35 of 90

- Adverse Events/Adverse Device Effects
- Any other significant reason identified by the Investigator.

For each case, information will be recorded in the source document and the electronic Case Report Form (eCRF) detailing circumstances leading to the withdrawal. Data collected upon point of withdrawal will be included as study data.

Subjects who drop out or are withdrawn will not be re-entered into the study at a later date. If at any point during the study, the total hip prosthesis needs to be revised for any reason the following will apply: Subjects shall continue to have follow-up visits in order to monitor the subject’s health status. Potential data following the revision surgery will not be included as study data but presented separately as safety data.

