8.4.3 Other Endpoints

The following exploratory endpoints will be collected:

- Dislocation percentage of the hip up to 2 years after device implantation.
- Hospital readmission percentage (cumulative) within 30, 60 and 90 days of discharge due to any reason related to study device or study procedure.

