7.12 Analysis of Exploratory Endpoints

Survivorship of compatible components up to 2 years

Survivorship of acetabular shell, femoral head, and any of the femoral stems will be estimated by cumulative proportion of hips without revision of the respective components due to any reason, up to 2 years. The cumulative implant survival rates will be summarized using KM product limit estimates. This will be summarized using the SAF analysis population.

Dislocation percentage of the hip up to 2 years after device implantation

The cumulative dislocation percentage at the interim visits up to 2 years after device implantation, $p_{dis,i}$ will be compared to a literature specified percentage, $p_{literature}$. These literature-specified

CONFIDENTIAL AND PROPRIETARY

This document contains information that is confidential and proprietary to Smith & Nephew PLC and Smith & Nephew, Inc. and is intended for use only by Smith+Nephew and its manufacturer. It shall not be reproduced or copied in whole or in part, nor shall the contents be disclosed by any means without prior written permission from Smith+Nephew, nor shall anyone make any use of it that is contrary to the expressed or implied wishes of Smith+Nephew.

Statistical Analysis Plan

A Prospective, Multi-center, Randomized, Controlled Study to Evaluate the
Safety and Efficacy of the OR3O[™] Dual Mobility System versus conventional
single bearing design Total Hip System in Primary Total Hip Arthroplasty (THA)Version: 2.0,
29-Feb-2024
Page: 25 of 27ProceduresProcedures

Number: OR3O.2019.10 ST: 1100 Version: 2.0, 29-Feb-2024 Page: 25 of 27

percentages will be specified prior to database lock for final analyses. For the estimation of dislocation rate, a hip with multiple dislocations on-study will be counted only once. Two-sided exact 95% CIs will be estimated for p_{dis,i} where i is the visit at which the cumulative dislocation will be estimated (i.e. at 3months, 6 months, 1 year and 2 years). This will be summarized using the SAF population. One of the following conclusions will be made:

- If the lower limit (LL) of the two-sided 95% CI for $p_{dis,i}$ is > $p_{literature}$, then it is concluded that the dislocation rate on-study is significantly greater than the literature-specified rate.
- If the upper limit (UL) of the two-sided 95% CI for $p_{dis,i} < p_{literature}$, then it is concluded that the dislocation rate on-study is significantly less than than the literature-specified rate.

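### Sections 7.8.1 and 7.8.2 conflict on follow-up after revision, and new events after an AE or illness withdrawal are not collected, which biases the dislocation percentage low

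*Protocol*

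**What the plan says.** **After revision.** Protocol 7.8.1 applies when "the study device needs to be revised for any reason the following will apply". It then states "Subjects will terminate the study following revision surgery" and leaves later care to the site's usual practice. Protocol 7.8.2 applies when "the total hip prosthesis needs to be revised for any reason the following will apply", and states "Subjects shall continue to have follow-up visits in order to monitor" the subject's health status. Both sections keep post-revision data out of the study data and present them separately as safety data. Section 7.8.1 adds that they are reported as follow-up to the adverse event.

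**Withdrawal by the investigator.** Protocol 7.8.2 lists reasons for which the investigator may withdraw a subject from the study. They include "Adverse Events/Adverse Device Effects" and concurrent illness. A withdrawn subject does not re-enter.

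**What is promised to 2 years.** Protocol 8.4.3 lists "Dislocation percentage of the hip up to 2 years after device implantation" as an endpoint, derived from the AE forms (9.2.4). SAP 7.12 also estimates survivorship of shell, head and stem as the "cumulative proportion of hips without revision of the respective components due to any reason, up to 2 years", by Kaplan-Meier. Both use the safety population, which SAP 7.2 defines as all implanted hips.

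**The concern.** There are two separate problems.

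First, a site with a revised patient finds two instructions for the same event and no cross-reference between them. One ends participation and the other continues visits.

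Second, withdrawing an implanted subject because of an AE removes no exposure, because the implant stays in place. It removes only observation. The decision rests with an investigator who may be the surgeon, and Protocol 8.2.2 accepts that the surgeon cannot be blinded. Loss of follow-up can therefore depend on how the patient is doing. At stake is whether the 2-year dislocation percentage and the survivorship curves describe all implanted hips or only those still being watched.

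**Working it through.** **Step 1: do the two revision rules overlap?** The triggers are worded differently (study device; total hip prosthesis). Protocol 9.2.1 counts insert and liner among the components whose revision ends THA survivorship, so a liner or insert revision meets both. Both rules cover revision for any reason. The overlap is real, and the instructions differ on whether visits go on.

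**Step 2: what does the conflict change for revised hips?**

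| | 7.8.1 | 7.8.2 |
|---|---|---|
| Participation | ends | visits continue |
| Later data in study data | no | no |
| Later data as separate safety data | yes | yes |

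The first revision is recorded before exit and is itself the survivorship event. The conflict therefore affects how much separately presented safety data exist after revision. It does not affect the study endpoints for that hip.

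**Step 3: what is collected after an AE or illness withdrawal?**
- Exit visit: Protocol 9.1.6 applies the end-of-study visit on withdrawal, and 9.1.9 asks for it where possible.
- Events open at exit: under 12.5.1, related events are followed until resolved or chronic, and unrelated events for at most 30 days.
- New events after exit: no section provides for them. The telephone contact in 9.1.4 to 9.1.6 is for missed visits, not for withdrawn subjects.

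**Step 4: how does that reach the estimates?** SAP 7.12 gives dislocation as a cumulative percentage of the safety population, counting each hip once, and states no adjustment for time observed. A hip that exits and later has a first dislocation stays in the denominator and is missing from the numerator, so the percentage can only be too low. Survivorship is estimated by Kaplan-Meier. The censoring rule (Protocol 10.4.2, SAP 7.11) names death, loss to follow-up and no event by study termination, but not investigator withdrawal. Censoring at such exits may be informative; the documents do not show in which direction.

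**Step 5: size.** Protocol 4.2 cites 0.9% dislocation in primary dual-mobility THA, with no time horizon.
- Expected events per arm: 0.009 × 85 = 0.77.
- Effect of one unseen event: 1/85 = 1.2 percentage points.
- Expected events missed = exits × risk after exit. The documents give no number of AE or illness exits. As an assumption, let 10% of 85 hips (8.5) exit from day 0. At a risk of 0.9%, 8.5 × 0.009 = 0.08 events, or 0.08/85 = 0.09 percentage points. At 4.6%, the figure in Protocol 4.2 for dual mobility in displaced femoral neck fracture, 8.5 × 0.046 = 0.39 events, or 0.39/85 = 0.46 percentage points.

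The 10% is borrowed only as a round figure. In Protocol 11.1 it is all-cause attrition at 1 year, not an allowance for AE exits. All of these figures use the planned 85 per arm; the SAP reports early termination without giving the number enrolled.

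**The case against.** Several stronger readings are tempting, and the documents do not support them.

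- A reader might infer that 2-year safety data stop for patients with problems. They do not: post-revision data are kept as safety data under both sections, withdrawal is optional, an exit visit is requested, and related open events are followed until resolved or chronic.
- A reader might infer that dislocation and component survivorship of revised hips would differ by site according to the section followed. Both sections exclude post-revision data from the study data, so this fails.
- A reader might think that a hip withdrawn because it dislocated is lost. It is already counted, since each hip counts once. Only a first event after exit for another reason is missed.
- The wording in 7.8.2 on monitoring health status is close to standard-of-care follow-up and does not say the protocol schedule continues. The conflict is thus narrower than the two sentences suggest, but it is not removed.
- SAP 7.6 already summarises reasons for non-completion and tabulates revised and terminated hips by visit, and Protocol 10.3 calls for a dropout comparison. Neither gives day of exit.
- SAP version 2.0 drops formal testing after early termination, so protocol wording can now change little. That stands. The descriptive dislocation percentage and the Kaplan-Meier estimates remain, however, and they are what readers will see.

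**Conclusion.** The contradiction between 7.8.1 and 7.8.2 is established from the text and needs one reconciled rule. The gap after AE or illness withdrawal is also established: first dislocations, first revisions and new AEs after exit may go unseen. For dislocation the direction is clear, because the denominator is all implanted hips and no adjustment for follow-up is stated. For survivorship, informative censoring is possible but its direction is not shown.

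The size is uncertain. Under the assumptions above, the expected understatement is about 0.1 to 0.5 percentage points, but with less than one event expected per arm at 0.9%, a single unseen event moves the result by 1.2 points. Selective exit could raise the expected loss; the documents give no figure for it. This review takes no position on which revision rule is right or on when an investigator should withdraw a subject.

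**What to change.** 1. **Protocol 7.8.1 and 7.8.2:** reconcile them into one statement of what happens to study participation and visits after revision, and apply it at all sites.
2. **Data collection after exit:** state that for implanted subjects who leave scheduled visits without withdrawing consent, implant status, dislocation and AEs are still collected to 2 years. The telephone contact in 9.1.4 to 9.1.6 already collects implant status and AEs; extending it to these subjects is a new use of an existing procedure.
3. **SAP 7.6:** tabulate exits for revision, AE and concurrent illness by arm, with day of exit.
4. **SAP 7.12:** show the dislocation percentage with the follow-up actually observed, or as a time-to-event estimate.

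The cost is protocol wording, a few extra calls and one table. Because the study ended early, items 3 and 4 have the most remaining effect.

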7.8.2 Withdrawal from Study

The Investigator may withdraw subjects from the study, including but not limited to the following reasons:

- Subject noncompliance (e.g., did not follow instructions for regular follow up);
- Subject lost to follow-up;
- The Investigator or the Sponsor stops the study for any reason and decides to withdraw subject(s) from the study;
- Concurrent illness;

CONFIDENTIAL AND PROPRIETARY

This document contains information that is confidential and proprietary to Smith & Nephew PLC and Smith & Nephew, Inc. and is intended for use only by Smith & Nephew and its manufacturer. It shall not be reproduced or copied in whole or in part, nor shall the contents be disclosed by any means without prior written permission from Smith & Nephew, nor shall anyone make any use of it that is contrary to the expressed or implied wishes of Smith & Nephew.

Clinical Protocol	Study Number: OR3O.2019.10 (China)
Prospective, Multi-center, Randomized, Controlled Study to Evaluate the Safety and Efficacy of the OR3O™ Dual Mobility System versus conventional single bearing design Total Hip System in Primary Total Hip Arthroplasty (THA) Procedures	Version: 1.0, 18Aug2020
	Page: 35 of 90

- Adverse Events/Adverse Device Effects
- Any other significant reason identified by the Investigator.

For each case, information will be recorded in the source document and the electronic Case Report Form (eCRF) detailing circumstances leading to the withdrawal. Data collected upon point of withdrawal will be included as study data.

Subjects who drop out or are withdrawn will not be re-entered into the study at a later date. If at any point during the study, the total hip prosthesis needs to be revised for any reason the following will apply: Subjects shall continue to have follow-up visits in order to monitor the subject’s health status. Potential data following the revision surgery will not be included as study data but presented separately as safety data.

7.8.3 Subject’s Withdrawal of Consent to Participate in Study

Study participation is voluntary, and subjects may withdraw at any point during the study without giving their reason for doing so. Where subjects withdraw consent, the Investigator should make a reasonable effort to ascertain the reason(s), while fully respecting the subject’s privacy. The reason for withdrawal will be recorded in the eCRF and source documents.

If withdrawal is after OR3O™ Dual Mobility System or controlled system implantation, then the Investigator should inform the subject of any recommended follow-up visits to monitor subject safety.

7.8.4 Use of Data Following Withdrawal

In cases where the subject withdraws consent, the data collected up to the point of withdrawal may be used, but no additional data for that subject may be collected after withdrawal of consent.

8. STUDY DESIGN

8.1 STUDY DESIGN AND JUSTIFICATION

This study is a prospective, multi-center, randomized, controlled, 2-arm study to assess safety and efficacy of the OR3O™ Dual Mobility System in Primary THA. Subjects meet the inclusion/exclusion criteria specified in the protocol will be randomized to receive implantation

CONFIDENTIAL AND PROPRIETARY

This document contains information that is confidential and proprietary to Smith & Nephew PLC and Smith & Nephew, Inc. and is intended for use only by Smith & Nephew and its manufacturer. It shall not be reproduced or copied in whole or in part, nor shall the contents be disclosed by any means without prior written permission from Smith & Nephew, nor shall anyone make any use of it that is contrary to the expressed or implied wishes of Smith & Nephew.

Clinical Protocol	Study Number: OR3O.2019.10 (China)
Prospective, Multi-center, Randomized, Controlled Study to Evaluate the Safety and Efficacy of the OR3O™ Dual Mobility System versus conventional single bearing design Total Hip System in Primary Total Hip Arthroplasty (THA) Procedures	Version: 1.0, 18Aug2020
	Page: 36 of 90

with the investigational product or controlled system. Up to 4 sites in China will participate competitive enrolling a total of 170 hips, whereas the number of subjects enroll in each study site should be no more than 85 cases.

The study is expected to enroll all subjects within a 12 months’ timeframe. Subjects will be followed-up at 6 weeks, 3, 6, 12 and 24 months after surgery.

In this study, a summary of 1 year follow-up data will be reported to NMPA for regulatory approval and a 2 year follow-up will be sufficient to identify and assess the risk of any associated unacceptable adverse event over this time period. The study duration will be sufficient to allow conclusions about likely safety and efficacy of the OR3O Dual Mobility System in a longer term.

[figure not shown]
Figure 8-1 details the different steps of study conduct from screening to enrollment and follow-up.

CONFIDENTIAL AND PROPRIETARY

This document contains information that is confidential and proprietary to Smith & Nephew PLC and Smith & Nephew, Inc. and is intended for use only by Smith & Nephew and its manufacturer. It shall not be reproduced or copied in whole or in part, nor shall the contents be disclosed by any means without prior written permission from Smith & Nephew, nor shall anyone make any use of it that is contrary to the expressed or implied wishes of Smith & Nephew.

Clinical Protocol	Study Number: OR3O.2019.10 (China)
Prospective, Multi-center, Randomized, Controlled Study to Evaluate the Safety and Efficacy of the OR3O™ Dual Mobility System versus conventional single bearing design Total Hip System in Primary Total Hip Arthroplasty (THA) Procedures	Version: 1.0, 18Aug2020
	Page: 37 of 90

Figure 8-1: Study Flowchart

Subjects may be assigned a subject ID, but then not enrolled in the study (e.g. did not receive the study or controlled device or decided not to participate in the study).

8.2 ALLOCATION AND BLINDING

8.2.1 Treatment Allocation

This study is randomized. All subjects who sign the ICF and meet inclusion / exclusion criteria will randomly receive either the OR3O™ Dual Mobility System in combination with R3™ and a Smith & Nephew Oxinium femoral head, or a conventional, single-bearing design Total Hip System comprised of R3™ Acetabular Shell with XLPE liner and a Smith & Nephew Oxinium femoral head at 1:1.

CONFIDENTIAL AND PROPRIETARY

This document contains information that is confidential and proprietary to Smith & Nephew PLC and Smith & Nephew, Inc. and is intended for use only by Smith & Nephew and its manufacturer. It shall not be reproduced or copied in whole or in part, nor shall the contents be disclosed by any means without prior written permission from Smith & Nephew, nor shall anyone make any use of it that is contrary to the expressed or implied wishes of Smith & Nephew.

Clinical Protocol	Study Number: OR3O.2019.10 (China)
Prospective, Multi-center, Randomized, Controlled Study to Evaluate the Safety and Efficacy of the OR3O™ Dual Mobility System versus conventional single bearing design Total Hip System in Primary Total Hip Arthroplasty (THA) Procedures	Version: 1.0, 18Aug2020
	Page: 38 of 90

8.2.2 Blinding

To minimize the impact of bias associated with treatment assignment during the study, since the surgeon cannot be blinded to the identity of the surgical product, it is planned to appoint an independent evaluator in each study site, who will be blinded and responsible for completing study related scoring at each follow-up.

8.3 DATA MANAGEMENT

8.3.1 Source Document

Investigators are responsible for obtaining and maintaining complete subject health information in the medical record for each subject (source documents). Source data is all information and original records of clinical findings, observations, or other activities necessary for the evaluation of the study. These original documents and data records include but are not limited to inpatient or outpatient medical records, clinical and office charts, laboratory notes, memoranda, subjects’ memory aids or evaluation checklists, transportation, delivery, use and recovery records of the device, recorded audio tapes of counseling sessions, recorded data from automated instruments, copies certified, microfiches, photographic negatives, microfilm or magnetic media, X-rays, and subjects’ files and records kept at the pharmacy, laboratories and ancillary departments involved in the clinical study. The AE and SAE Report Forms contain information other than medical records will be considered as the source document.

